# **Study Protocol with Statistical Analysis Plan**

The effect of additional neurodynamic intervention  
in patients with chronic ankle instability

NCT number: NCT05090423

Authors: [name], [name]

Department of Physical Therapy and Assistive Technology, National Yang  
Ming Chiao Tung University

July 22, 2024

**Background:** Chronic ankle instability (CAI) is characterized by pain, repeated sprains and giving way. Approximately 40% of acute ankle sprain would develop into chronic ankle instability. Recently, the pathomechanical impairment, sensory-perceptual impairment and motor-behavioral impairment have been documented in the chronic ankle instability model. Previous research revealed that compared to the control subjects, people with CAI had lower pressure pain threshold (PPT). This increased mechanosensitivity of the neural tissues around the ankle might account for pain and dysfunction in people with CAI. Pahor et al., indicated that in subjects following ankle inversion sprain there is greater restriction of knee extension on the injured side compared to non-injured side in the slump test with the ankle plantar flexion and inversion, which may suggest the restriction in mobility of the common peroneal tract. However, the effects of neurodynamic intervention, which addresses the mechanosensitivity problems, in people with CAI are still unclear. **Purpose:** The aim of the study is to investigate the effects of neurodynamic intervention on the mechanosensitivity, balance performance and self-reported function in patients with CAI. **Study design:** A randomized controlled trial design. Single-blinded. **Methods:** Forty subjects between 20-50 with CAI were recruited and randomized into either the exercise only group or the neurodynamic intervention with exercise (neurodynamic) group. The sample size was calculated based on the PPT data of Lorenzo-Sanchez-

Aguilera et al's, which requires 20 subjects in each group to reach a statistical power of 0.8. Both groups were receive 12 interventions within 6-8 weeks. The exercise only group performed balance training, while the neurodynamic group received balance training and neurodynamic intervention for the common peroneal nerve. Outcome measures included demographic data, pressure pain threshold, active knee extension range of motion (ROM) of the slump test with ankle plantarflexion and inversion (AKEOST), hamstrings flexibility, ankle range of motion, Y balance test and foot and ankle ability measure (FAAM). All data were assessed and collected before and after 12 interventions. **Statistics analysis:** Two-way repeated measures analysis of variance (ANOVA) was used to examine the intervention effect with the alpha level set at 0.05.

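### Does the stated power of 0.8 fail because the 40 subjects randomised leave no margin for loss?

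*Combined protocol and SAP*

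**What the plan says.** The relevant text is all in the Methods and Statistics analysis paragraphs of the combined protocol and SAP.

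- **Number randomised:** "Forty subjects between 20-50 with CAI were recruited and randomized", to exercise alone or to exercise with neurodynamic intervention.
- **Basis of the sample size:** "The sample size was calculated based on the PPT data of" an earlier study, "which requires 20 subjects in each group to reach a statistical power of 0.8". No effect size, standard deviation, sidedness or test is given for the calculation.
- **Treatment period:** "12 interventions within 6-8 weeks" in both groups, with outcomes measured before and after the course.
- **Analysis:** a two-way repeated measures ANOVA, which "was used to examine the intervention effect with the alpha level set at 0.05".

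The documents state no dropout rate, inflation of the sample, replacement rule, analysis population or method for missing data.

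**The concern.** A sample size calculation normally gives the number of subjects who must contribute data. Enrolment is then set higher to cover those who drop out. Here the required number and the number randomised are the same.

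The two measurements are separated by a course of twelve sessions over several weeks, so some loss is plausible. A standard repeated measures ANOVA drops anyone without the second measurement. With two groups and two occasions, the group-by-time test is equivalent to a two-sample t-test on the change scores, and a subject with no post value has no change score.

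On that view the only power figure in the document is a ceiling. Any loss would lower the power for PPT, the outcome the trial was sized on, and a reader might take a non-significant PPT result as stronger evidence of no effect than it is.

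**Working it through.** **1. Do the two numbers agree?** Required: 20 per group. Randomised: 40. Since 2 × 20 = 40, they agree, and the allowance for loss is 40 − 40 = 0. There is no arithmetic error.

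**2. Can the 20 per group be reproduced?** Not forwards, because the effect size and standard deviation are not given. The standardised difference d has to be solved backwards from the stated result. Assumptions: two-sample t-test, two-sided alpha 0.05, equal groups.

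Power = P(T′ > t₀.₉₇₅,df), where T′ is noncentral t with df = 2n − 2 and noncentrality d / √(2/n).

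Setting n = 20 and power = 0.80 gives d = 0.909. Check: df = 38, noncentrality = 0.909 / √0.1 = 2.87, power 0.800.

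**3. Power at smaller n, holding d = 0.909.** The loss rates are assumptions.

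| Per group with both assessments | Loss | Noncentrality | Power |
|---|---|---|---|
| 20 | 0% | 2.87 | 0.800 |
| 19 | 5% | 2.80 | 0.778 |
| 18 | 10% | 2.73 | 0.755 |
| 17 | 15% | 2.65 | 0.729 |
| 16 | 20% | 2.57 | 0.701 |
| 15 | 25% | 2.49 | 0.671 |

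The fall is 0.800 − 0.755 = 0.045 at 10% loss and 0.800 − 0.701 = 0.099 at 20%.

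**4. Sensitivity to the unstated inputs.** Each variant is recalibrated to 0.80 at 20 per group.

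| Variant | Implied d | Power at 18 | Power at 16 |
|---|---|---|---|
| Two-sided t | 0.909 | 0.755 | 0.701 |
| Two-sided normal | 0.886 | 0.757 | 0.707 |
| One-sided t | 0.801 | 0.761 | 0.715 |

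The fall in power is stable across variants. The implied d is not: it ranges from 0.80 to 0.91. For the planned ANOVA, d is measured against the standard deviation of change, which depends on a pre-post correlation that is not given.

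**5. Rounding.** Sample sizes are rounded up. If the exact requirement was just over 19 per group, d is up to 0.934 (two-sided t). Power is then up to 0.821 with 20 and 20, 0.810 with 20 and 19, and 0.777 with 18 and 18. One loss need not take power below 0.80. Two losses per group do so in every variant tried.

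**6. What an allowance would have required.** To keep 20 per group after a loss rate L, randomise 20 / (1 − L) per group. At 10%, 20 / 0.9 = 22.2, so 23 per group (46 in all). At 20%, 20 / 0.8 = 25 per group (50 in all).

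**The case for a change.** The strongest case for acting is that the sentence ties "20 subjects in each group" directly to the power, so the natural reading is that 20 must be analysed, and nothing suggests that a margin is already built in. The decline in power does not depend on the unstated sidedness. The implied detectable difference is already large, at about 0.9 standard deviations on the two-sided t-test, and losses push it up. One sentence saying that 0.80 assumes complete data would cost almost nothing.

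Part of this stands. No allowance is stated, and appreciable loss would reduce power by the amounts shown. Three things limit its force.

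- The documents do not say whether 20 means enrolled or analysed. They also do not say that a subject who misses sessions goes unassessed. Only a missing post assessment removes a subject from the ANOVA.
- No loss is documented. The text, written mainly in the past tense and dated July 2024, says that all data were collected at both time points. It gives no participant flow, so this is not proof of complete follow-up, but it offers no basis for a 10% or 20% rate.
- A caveat quoting detectable differences at 18 or 16 per group would put figures into the plan from a back-solved t-test. The sponsor's own inputs, which are not shown, might contradict them.

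**Conclusion.** The concern identifies a missing detail, not an error. The 40 subjects randomised supply the group size on which the stated power rests, and the documents do not show that power to be wrong.

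The possible cost is modest: about 4 to 5 points of power at 10% loss and 8 to 10 points at 20%. It rests on assumed loss rates and on a test calibrated to 0.80 at exactly 20 per group. It would be too strong to say that the figure holds only with no loss at all, since rounding may cover one lost subject.

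No change follows because nothing would be gained. Recruitment is described as done, so an enrolment margin is no longer a practical option. A qualifying sentence would leave the enrolment, the ANOVA and its result as they are. What a reader needs in order to judge a non-significant PPT result is the number per group with both assessments and the confidence interval for the group difference in change. Both are ordinary content of a results report and need no amendment to the plan.

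### Without a sham in the control arm, can the trial still answer the question its Purpose asks?

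*Combined protocol and SAP*

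**What the plan says.** The title of the combined protocol and SAP names the question as "The effect of additional neurodynamic intervention". The Purpose is to "investigate the effects of neurodynamic intervention on the mechanosensitivity, balance performance and self-reported function in patients with CAI". The Methods give the two arms: "The exercise only group performed balance training, while the neurodynamic group received balance training and neurodynamic intervention for the common peroneal nerve". They also fix the number of sessions: "Both groups were receive 12 interventions within 6-8 weeks". Session length and contact time per arm are not given. No sham technique, placebo component or attention control is described for the exercise only group.

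On blinding, the Study design entry says only: "A randomized controlled trial design. Single-blinded". It does not say whether the participant, the assessor or someone else was blinded.

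The neural rationale is in the Background, which ends its argument by noting that "the effects of neurodynamic intervention, which addresses the mechanosensitivity problems, in people with CAI are still unclear". PPT, the source of the sample size, and FAAM are both among the outcomes.

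**The concern.** One arm receives what the other receives plus one more treatment. Any difference between them is then the sum of whatever the neurodynamic technique does to the nerve and whatever an additional treatment does through attention and expectation. PPT is a threshold the participant indicates and FAAM is self-reported, so both are open to the second route.

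Single blinding does not clearly close it. If only the assessor was blinded, participants may have known that they received an extra therapy. If only the participant was blinded, the assessor-scored measures are exposed instead.

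The Purpose, unlike the title, does not call the intervention additional. Read straight after a Background built on mechanosensitivity, it could suggest that a PPT gain will be taken as proof of a neural effect. At stake is over-interpretation of a positive result. A natural remedy would be to reword the Purpose, rule out a neural reading of PPT and FAAM, and declare the assessor to be the blinded party.

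**Working it through.** **1. The plan's own figure.** The document states 20 per group for power 0.8, based on PPT data from a cited study, and gives neither a difference nor an SD. The figure cannot be reproduced, but the standardised difference it implies can be solved for. With two-sided alpha 0.05 (sidedness is not stated, so this is an assumption):

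d = (1.960 + 0.842) × √(2/20) = 2.802 × 0.3162 = 0.886 by the normal approximation, or 0.909 by the t-test.

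The one-sided equivalents are 0.786 and 0.801. None of these values bears on the choice of comparator.

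**2. What the contrast estimates.** Let A be the effect of balance training, S the specific effect of the neurodynamic technique and N any non-specific effect of receiving it. The exercise only arm has expected change A. The other arm has A + S + N. The randomised difference is

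(A + S + N) − A = S + N,

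assuming the effects add. This is the effect of adding the component to balance training. S cannot be separated from N without a sham or attention-matched arm.

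**3. What the document claims.** Setting the places side by side:

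| Place | What it asks or asserts |
|---|---|
| Title | Effect of the additional intervention: S + N |
| Purpose | Effects of the intervention on three outcome domains, mechanosensitivity being one of them: answerable as S + N |
| Methods | Arms defined as exercise only, and exercise with the neurodynamic component: S + N |
| Background | Tentatively worded neural rationale; no hypothesis that S alone will be tested |

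No entry claims to isolate S, and the document contains no planned conclusion that would need correcting.

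**4. Size of the possible non-specific effect.** With one measurement before and one after, the group-by-time test in the two-way repeated measures ANOVA is equivalent to a two-sample t-test on change scores. The probability of rejection at n = 20 per group depends on the noncentrality d × √(n/2) = d × √10 = 3.162d. Setting S = 0 and letting N take assumed values in SDs of change, at two-sided alpha 0.05:

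| Assumed N (SD of change) | Noncentrality | Probability of p < 0.05 |
|---|---|---|
| 0 | 0 | 5.0% |
| 0.1 | 0.316 | 6.1% |
| 0.2 | 0.632 | 9.5% |
| 0.3 | 0.949 | 15.2% |
| 0.4 | 1.265 | 23.4% |
| 0.5 | 1.581 | 33.8% |

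None of the values of N comes from the documents.

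**5. How to read those percentages.** They exceed 5% only as error rates for the hypothesis S = 0. For the hypothesis S + N = 0, which the title and arms set up, a rejection when N = 0.5 SD is correct, and 33.8% is simply the power to detect that difference.

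**The case for a change.** The best case for a change is that the wording invites misreading. The Background moves from lower PPT, to sensitive neural tissue, to a treatment aimed at it. The Purpose then puts mechanosensitivity first among its outcomes and drops the title's qualifier. PPT is both the outcome behind the sample size and one that depends on participant response. AKEOST is an active range, so it depends on the participant too. A few sentences would guard against over-reading at almost no cost.

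Part of this stands. The trial cannot support a claim of specific neural action, and a report that made one would go beyond the design. It is also fair to want the report to say who was blinded and how much contact time each arm had.

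The rest does not lead to a change. The harm lies in a reader's possible mistake, not in anything the plan does. The qualifier missing from the Purpose is in the title and is built into the arm names. The natural remedy would also add facts the document does not contain. Both arms have the same number of sessions and unequal contact time is not documented, so extra therapist contact can be suspected but not asserted. Declaring the assessor to be the blinded party could be untrue. The document is written largely in the past tense, which suggests that the identity of the blinded party is by now a matter of fact to be reported, not a choice to be made.

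**Conclusion.** No change to the plan follows. A comparison of balance training with and without the neurodynamic component is a legitimate randomised design. It answers the add-on question in the title, which is also the natural reading of the Purpose. Its price is that the estimate includes any non-specific effect on participant-dependent outcomes such as PPT and FAAM. That is a fair trade-off for a two-arm trial of 40 people and is visible from the description of the arms.

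The size of the non-specific part cannot be determined from the documents. The 9.5% to 33.8% range rests wholly on assumed shifts of 0.2 to 0.5 SD of change with no specific effect, a two-sided test and 20 analysed per group. It describes power for the add-on effect and does not show an inflated error rate for the question asked.

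The unnamed blinded party and the unstated contact time are missing details that the authors can supply when they report. Repeating the title's qualifier in the Purpose would be an editorial courtesy that leaves every procedure, test and result as it is. The conclusion would differ if the document claimed to isolate a neural mechanism, but it does not.

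### The planned repeated-measures ANOVA on one pre and one post value is valid, but ANCOVA on the baseline already collected would usually be more precise

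*Combined protocol and SAP*

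**What the plan says.** The combined protocol and SAP is a short structured text. Four of its statements bear on this point.

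- **Design (Methods).** "Forty subjects between 20-50 with CAI were recruited and randomized into either the exercise only group" or the neurodynamic-plus-exercise group. Both groups do balance training; the arms differ only in the added component: "while the neurodynamic group received balance training and neurodynamic intervention for the common peroneal nerve".
- **Timing (Methods).** "All data were assessed and collected before and after 12 interventions". Each outcome therefore has one baseline and one post-treatment value per patient.
- **Sample size (Methods).** It rests on pressure pain threshold data from an external study, "which requires 20 subjects in each group to reach a statistical power of 0.8". The difference, SD and correlation behind it are not given.
- **Analysis (Statistics analysis).** "Two-way repeated measures analysis of variance (ANOVA) was used to examine the intervention effect with the alpha level set at 0.05". This is the whole analysis text. It names no covariate, no baseline adjustment and no second analysis, and it does not say which ANOVA term carries the intervention effect.

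**The concern.** With two groups and two time points, the group-by-time F statistic is the square of the t statistic comparing mean change between groups. A change score subtracts the whole baseline value, which amounts to assuming a baseline coefficient of exactly 1. Unless the true slope of post on baseline is close to 1, that over- or under-corrects and adds noise. ANCOVA of the post value on group and baseline estimates the slope from the same 40 patients.

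What is at stake is precision, not bias or type I error. The trial is small, its stated power is 0.8 for pressure pain threshold alone, and the purpose also covers balance and self-reported function, for which no power is given. Precision that the trial's own baseline data could supply is worth having here.

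**Working it through.** **Inputs from the document:** 20 patients per group, alpha 0.05, one pre and one post value, stated power 0.8. **Assumed, because not given:** two-sided testing, bivariate normal data, the same slope in both arms, no missing data, a range for the pre/post correlation ρ, and a range for k = post SD / pre SD.

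**1. The plan's own figure.** The 20 per group cannot be reproduced without a difference and an SD. Solved backwards, 20 per group at 80% power implies a standardised difference of √(2/20) × (1.960 + 0.842) = 0.886 by the normal approximation, or 0.909 by the t-test on 38 degrees of freedom.

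**2. Equivalence.** On one simulated data set of 40, the group-by-time F and the squared change-score t were both 0.43407.

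**3. Variance formulas.** With the pre SD as unit, the variance per patient is:

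- change score: k² + 1 − 2kρ
- ANCOVA residual: k²(1 − ρ²)

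The first minus the second is (1 − kρ)², which is never negative. This excess is the noise that chance baseline imbalance adds to the change-score comparison, so sensitivity to imbalance is the same loss and must not be counted twice. Estimating the slope costs ANCOVA a factor of 1 + 1/(40 − 4) = 1.028. Hence

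ratio = 1.028 × k²(1 − ρ²) / (k² + 1 − 2kρ).

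Example, k = 1 and ρ = 0.5: 0.75 / 1.00 × 1.028 = 0.771. The confidence interval is then about √0.771 = 0.88 times as wide, or 12% narrower.

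**4. Variance ratio, ANCOVA to change score** (below 1 favours ANCOVA).

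| ρ | k = 0.8 | k = 1 | k = 1.2 |
|---|---|---|---|
| 0.3 | 0.516 | 0.668 | 0.783 |
| 0.5 | 0.587 | 0.771 | 0.895 |
| 0.7 | 0.645 | 0.874 | 0.993 |
| 0.9 | 0.625 | 0.976 | 1.004 |
| 0.95 | 0.534 | 1.002 | 0.902 |

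The ratio exceeds 1 for ρ above 0.946 when k = 1, for ρ between 0.717 and 0.904 when k = 1.2, and never when k = 0.8. Its maximum is 1.028, reached where kρ = 1. With k = 1, the interval-width ratios at ρ = 0.3, 0.5, 0.7 and 0.9 are 0.818, 0.879, 0.936 and 0.989.

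**5. Power, k = 1.** Two illustrative anchors are used, because the plan does not say what the 0.8 refers to.

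| ρ | A: change score | A: ANCOVA | B: change score | B: ANCOVA |
|---|---|---|---|---|
| 0.3 | 80% | 93% | 66% | 83% |
| 0.5 | 80% | 89% | 80% | 89% |
| 0.7 | 80% | 85% | 95% | 97% |
| 0.9 | 80% | 81% | about 100% | about 100% |

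Anchor A sets the effect so that the change-score test has 80% power at every ρ. Anchor B fixes the raw effect at 0.909 SD.

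**6. Validity.** In simulations of 40,000 trials per setting (k = 0.8, 1 and 1.2; ρ from 0.3 to 0.9), type I error was 4.8% to 5.2% and absolute bias at most 0.004 SD for both methods. At k = 1 the simulated variance ratios were 0.672, 0.768, 0.870 and 0.980, close to the formula.

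**The case against.** The strongest reply is that nothing in the plan is wrong. Group-by-time ANOVA is an accepted analysis of randomised pre/post data, and the loss cannot be shown for this trial because ρ, the SDs and the effect size are absent. The gain can be negligible: with k = 1.2 under anchor A, ANCOVA power is about 89% and 84% at ρ of 0.3 and 0.5, but about 80% at 0.7 and 0.9. (With k = 0.8 it is 94% to 97%.) The stated 0.8 is not tied to change scores either. Finally, the text is in the past tense, so a change of primary analysis may come too late.

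Most of this stands as a limit on the claim: it is about efficiency only, its size is conditional, and a late ANCOVA would not alter the power of the planned test. It does not remove the point, because the trade is uneven: at most 2.8% of variance lost, against a reduction of about 13% to 33% at ρ of 0.3 to 0.7 with equal SDs.

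A further objection is that the unnamed ANOVA term matters more. Under anchor A, reading the effect from the group main effect, which averages in the baseline and so halves the difference, would give simulated power of about 54%, 37%, 22% and 10% at ρ of 0.3, 0.5, 0.7 and 0.9. The time main effect would not compare the groups at all. Because the arms differ only by the added intervention, group-by-time is the natural reading, but the plan should say so.

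**Conclusion.** The point holds as a missed efficiency. The only analysis named is valid, but it usually gives up precision that the collected baseline would supply. With equal SDs the loss is material at low to moderate correlation, small at 0.9, and gone near 0.94 to 0.95. With a smaller post SD (k = 0.8) ANCOVA gains at every correlation; with a larger one (k = 1.2) there is a band with no gain. These conclusions assume that the effect is read from group-by-time, that the data are near-normal with a common linear slope, and that nothing is missing. The change is worth making, but the planned test does not invalidate the trial. Confidence in the size is moderate, since ρ and k must be assumed.

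**What to change.** For each continuous outcome, specify:

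> The intervention effect is the between-group difference in the post-intervention value, estimated by ANCOVA with group as factor and the baseline value of the same outcome as covariate, and reported with a 95% confidence interval.

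If outcome data have already been examined, keep the ANOVA as the planned test, report the ANCOVA alongside it, and state that it was added later. If the ANOVA is kept in any role, state that the group-by-time term is the test of the intervention effect.

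The cost is one residual degree of freedom and, at worst, 2.8% in variance. No further patients, visits or measurements are needed. The linear, common-slope assumption should be checked for each outcome, since the outcomes differ in kind.
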